## 7.2 STATISTICAL ANALYSES

In the PFS, ToT and OS, Kaplan-Meier survival distribution functions will be estimated. Hence, if possible median PFS, ToT and OS as well as interquartile ranges (IQR) will be estimated. Unadjusted Kaplan Meier curves will be presented to illustrate time-to-event (PFS, ToT or OS).

For OS, OS-rates (%) at 6, 12 and 24-months (landmarks) will be estimated.

For the descriptive statistics, numbers and percentages will be provided and presented in tables, including cross tabulations (see section 8 for presentation of tables shells).

For

- 'all patients' vs. 'patients younger than 50 years'
- 'all patients' vs. 'patients aged 50-70 years'
- 'all patients' vs. 'patients older than 70 years'

statistical test (e.g.  $\chi^2$ -test) for differences in:

- 'types of metastases' (visceral, non-visceral or both)
- 'surgery' (yes or no)

will be performed.

All data analysis will be executed using statistical software such as SAS or Rstudio.

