8.1. Definitions

PFS is defined as the date of relapse or stage IV disease (index date) to progression or death, whichever occurs first.

- Patients will be censored for PFS by 31 December 2020
- Progression of disease is based on scans and blood testing results

ToT is defined as date of palbociclib treatment start to date of treatment stop with palbociclib.

OS is defined as the date of relapse or stage IV disease (index date) until death of any cause

- Patients will be censored for OS by 01 May 2022
- Overall survival will also be reported after 6, 12 and 24 months (*landmark cut-off time points*)

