9.5.1. Sub-groups

In addition, the primary objective (PFS, ToT) as well as some of the secondary objectives (OS and first subsequent post-palbociclib treatment) will be addressed for the following sub-groups such as those below provided sample size is sufficient:

- Specific age groups (below 50 years, 50 -70, and above 70 years of age)
- Patients with visceral disease (defined as metastases in the organs, eg, lung, liver)

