## 4.1 SUBGROUPS

*For the population of patients with HR+/HER2- locally advanced or MBC treated with palbociclib, results will also be presented for the following subgroups:*

- *Patients younger than 50 years*
- *Patients aged 50-70 years*
- *Patients older than 70 years*
- *Patients with visceral disease (defined as metastases in the organs, e.g., lung, liver)*
- *Patients without visceral disease (defined as metastases in the organs, e.g., lung, liver)*

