### 7.1 DEFINITIONS

Incidence date	The date of the initial breast cancer diagnosis
Index date	The date of relapse or stage IV disease
Progression Free Survival (PFS)	The time from the date of relapse or stage IV disease (index date) to progression or death, whichever occurs first. Patients will be censored 31 December 2020. Progression of disease is based on scans and blood testing results.
Overall Survival (OS)	The time from index date to death of any cause.
Time on Treatment (ToT)	The date of palbociclib treatment start to date of treatment stop with palbociclib. ToT is estimated on the basis of variables RE203-RE205 and RE206-RE208 in the DBCG database
Visceral disease	Defined as metastases in the organs, i.e., liver, lung, ascites, pleural effusion, and metastases in the central nervous system. Visceral disease is based on the variable Location of metastases (RE10-18 + 80-81, 117-119, 219-222) in the DBCG database

PFIZER CONFIDENTIAL

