	Adjuvant treatment*	Type 1: Median number of treatments of type 1: Type 2: Median number of treatments of type 2:

PFIZER CONFIDENTIAL

All included patients	Visceral metastases	Type of MBC	Primary MBC: N (%) Recurrent MBC: N (%)
		Number of metastases	0: N (%) 1: N (%) 2: N (%) >2: N (%)
		Location of metastases	Skin: N (%) Bone: N (%) Lung: N (%) Liver: N (%) CNS: N (%) Other: N (%)
		Surgery	Yes: N (%) No: N (%)
		Adjuvant treatment*	Type 1: Median number of treatments of type 1: Type 2: Median number of treatments of type 2:
Non-visceral metastases		Type of MBC	Primary MBC: N (%) Recurrent MBC: N (%)
		Number of metastases	0: N (%) 1: N (%) 2: N (%) >2: N (%)
		Location of metastases	Skin: N (%) Bone: N (%) Lung: N (%) Liver: N (%) CNS: N (%) Other: N (%)
		Surgery	Yes: N (%) No: N (%)
		Adjuvant treatment*	Type 1: Median number of treatments of type 1: Type 2: Median number of treatments of type 2:
		Time from initial breast cancer diagnosis (incidence date) to relapse	Median time

\* The result may be more than 2 types of adjuvant treatment.

PFIZER CONFIDENTIAL

**Table 4.** Progression Free Survival (PFS)\*

Endpoint	Population	Subgroup	Outcome	Result
Primary	Included patients treated with palbociclib in combination with AI	-	PFS	Median and IQR
Primary	Included patients treated with palbociclib in combination with AI	Patients younger than 50 years	PFS	Median and IQR
		Patients aged 50-70 years	PFS	Median and IQR
		Patients older than 70 years	PFS	Median and IQR
Primary	Included patients treated with palbociclib in combination with AI	Patients with visceral disease	PFS	Median and IQR
		Patients without visceral disease	PFS	Median and IQR
Secondary	Included patients treated with palbociclib in combination with Fulvestrant	-	PFS	Median and IQR
Secondary	Included patients treated with palbociclib in combination with Fulvestrant	Patients younger than 50 years	PFS	Median and IQR
		Patients aged 50-70 years	PFS	Median and IQR
		Patients older than 70 years	PFS	Median and IQR
Secondary	Included patients treated with palbociclib in combination with Fulvestrant	Patients with visceral disease	PFS	Median and IQR
		Patients without visceral disease	PFS	Median and IQR

Table note: \* Following definition of PFS in section 7.1.

**Table 5.** Time on Treatment (ToT)\*

Endpoint	Population	Subgroup	Outcome	Result
Primary	Included patients treated with palbociclib in combination with AI	-	ToT	Median and IQR

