Primary	Included patients treated with palbociclib in combination with AI	Patients younger than 50 years	ToT	Median and IQR
		Patients aged 50-70 years	ToT	Median and IQR
		Patients older than 70 years	ToT	Median and IQR
Primary	Included patients treated with palbociclib in combination with AI	Patients with visceral disease	ToT	Median and IQR
		Patients without visceral disease	ToT	Median and IQR
Secondary	Included patients treated with palbociclib in combination with Fulvestrant	-	ToT	Median and IQR
Secondary	Included patients treated with palbociclib in combination with Fulvestrant	Patients younger than 50 years	ToT	Median and IQR
		Patients aged 50-70 years	ToT	Median and IQR
		Patients older than 70 years	ToT	Median and IQR
Secondary	Included patients treated with palbociclib in combination with Fulvestrant	Patients with visceral disease	ToT	Median and IQR
		Patients without visceral disease	ToT	Median and IQR

Table note: \* Following definition of ToT in section 7.1.

**Table 6.** Overall Survival (OS)\*

Endpoint	Population	Subgroup	Outcome	Result
Secondary	Included patients treated with palbociclib in combination with AI	-	OS	Median and IQR OS-rates (%) at 6, 12 and 24-months
Secondary	Included patients treated with palbociclib in combination with AI	Patients younger than 50 years	OS	Median and IQR OS-rates (%) at 6, 12 and 24-months
		Patients aged 50-70 years	OS	Median and IQR OS-rates (%) at 6, 12 and 24-months
		Patients older than 70 years	OS	Median and IQR OS-rates (%) at 6, 12 and 24-months
Secondary	Included patients treated with palbociclib in combination with AI	Patients with visceral disease	OS	Median and IQR OS-rates (%) at 6, 12 and 24-months
		Patients without visceral disease	OS	Median and IQR OS-rates (%) at 6, 12 and 24-months
Secondary	Included patients treated with palbociclib in combination with Fulvestrant	-	OS	Median and IQR OS-rates (%) at 6, 12 and 24-months
Secondary	Included patients treated with palbociclib in combination with Fulvestrant	Patients younger than 50 years	OS	Median and IQR OS-rates (%) at 6, 12 and 24-months
		Patients aged 50-70 years	OS	Median and IQR OS-rates (%) at 6, 12 and 24-months
		Patients older than 70 years	OS	Median and IQR OS-rates (%) at 6, 12 and 24-months
Secondary	Included patients treated with palbociclib in combination with Fulvestrant	Patients with visceral disease	OS	Median and IQR OS-rates (%) at 6, 12 and 24-months

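### No confidence interval is planned for any PFS, ToT or OS estimate in a study whose only product is estimates; secondarily, PFS is censored 16 months before OS with no reason given

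*SAP*

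**What the plan says.** **Output.** SAP 7.2 plans Kaplan-Meier estimation for PFS, ToT and OS: "if possible median PFS, ToT and OS as well as interquartile ranges (IQR) will be estimated". It adds OS rates at three landmarks and unadjusted curves. In the shells, the result column of Table 4 (PFS) and Table 5 (ToT) reads "Median and IQR", and that of Table 6 (OS) reads "Median and IQR OS-rates (%) at 6, 12 and 24-months". No interval, confidence band, number at risk or row N is specified. Protocol 9.7 adds none. In both documents, confidence intervals appear only in the protocol's abbreviation list and in results cited from other studies.

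**Purpose.** Protocol 9.1 and SAP 3 describe a descriptive, exploratory study without hypothesis tests.

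**Subgroups.** Protocol 9.5.1 makes subgroup work conditional: outcomes "will be addressed for the following sub-groups such as those below provided sample size is sufficient". No threshold is given. SAP 4.1 says only that "results will also be presented for the following subgroups" and does not repeat the condition.

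**Dates.** Protocol 8.1: "Patients will be censored for PFS by 31 December 2020". SAP 7.1: "Patients will be censored 31 December 2020". That is also the last permitted palbociclib start date (Protocol 9.2.1). Protocol 8.1 censors OS on 1 May 2022, but the OS definition in SAP 7.1 has no date. Neither document gives a cut-off for ToT, which is also a primary endpoint. Protocol 9.2 sets a 2017–2020 study period and extends follow-up for OS only, without saying why.

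**The concern.** A descriptive study is useful to the extent that readers can judge how firmly each number is known. The planned tables do not let them. A median from a large cohort and one from a small age group would be printed in the same form.

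The rest of the plan does not supply the missing information. Tables 4–6 have 36 result rows (12 each), of which 30 are subgroups, and none carries an N. Table 2 counts patients by age, visceral status and type of MBC, but not by AI or fulvestrant, so the size behind a given row cannot be recovered. The sponsor receives summary tables only (Protocol 9.6), so the shells largely decide what is delivered.

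The PFS date compounds this for a primary endpoint. Patients who started late in 2020 contribute almost no follow-up on treatment to PFS, yet at least 16 months to OS.

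**Working it through.** **No planned figure to reproduce.** The 1,500 patients in Protocol 9.5 are a register estimate with no precision target behind them. The dates can be checked. From 31 December 2020 to 1 May 2022 is 16.0 months. From 1 January 2017 to 1 May 2022 is 5.33 years, against the protocol's close to 5.5.

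**Inputs from the protocol.** Median PFS with palbociclib plus letrozole: 20.0 (real-world), 24.8 and 27.6 months (phase 3, first report and extended follow-up), all in section 7. Start window: 48 months (9.2.1).

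**Assumptions, not in the documents.** Exponential PFS counted from palbociclib start; uniform starts; administrative censoring only; n = 1,000 for the AI cohort and n = 150 for a subgroup, because neither size is given.

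**Formulae.** λ = ln 2 / median. G(u) is the share of patients with potential follow-up beyond u. Follow-up runs 0–48 months at the 2020 cut and 16–64 months at 1 May 2022. With Greenwood's variance,

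I = ∫₀^median λ·e^(λu)/G(u) du, and half-width of the median = 1.96·√(I/n)/λ.

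Example, median 20.0, 2020 cut: λ = 0.03466 and I = 1.334. At n = 1,000, 1.96 × √0.001334 / 0.03466 = 2.07 months. At n = 150, 1.96 × √(1.334/150) / 0.03466 = 5.33 months.

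| True median (months) | 20.0 | 24.8 | 27.6 |
|---|---|---|---|
| I, 2020 cut | 1.334 | 1.466 | 1.562 |
| Half-width, n = 1,000, 2020 cut | 2.07 | 2.69 | 3.08 |
| Half-width, n = 150, 2020 cut | 5.33 | 6.93 | 7.96 |
| I, 1 May 2022 cut | 1.012 | 1.048 | 1.077 |
| Half-width, n = 1,000, 1 May 2022 | 1.80 | 2.27 | 2.56 |
| Half-width, n = 150, 1 May 2022 | 4.64 | 5.86 | 6.61 |
| Ratio of widths, 2020 to 2022 | 1.148 | 1.183 | 1.204 |

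In simulation at n = 150 with the 2020 cut, the upper confidence limit was not reached in 0.3%, 10.0% and 27.5% of data sets. The 8.0-month figure is therefore only a guide.

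**OS rates.** Taking the protocol's 2–3 years as medians of 24 to 36 months, the 24-month OS rate at the 1 May 2022 cut carries about ±3 percentage points at n = 1,000 and ±8 at n = 150.

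**Events lost to the earlier PFS cut.** Expected event share = 1 − [e^(−λx) − e^(−λ(48+x))]/(48λ), with x = 0 or 16. Per 1,000 patients:

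| Median | Events, 2020 cut | Events, 1 May 2022 | Lost |
|---|---|---|---|
| 20.0 | 513 | 720 | 207/720 = 29% |
| 24.8 | 449 | 648 | 199/648 = 31% |
| 27.6 | 419 | 611 | 192/611 = 31% |

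**Upper quartile of the planned IQR.** For an exponential this is twice the median: 40.0, 49.6 and 55.2 months, against at most 48 months of follow-up at the 2020 cut. In 1,000 simulated data sets per case at n = 1,000, it was reached in 96%, 31% and 10% at the 2020 cut, and in 100%, 100% and 95% at 1 May 2022.

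**Sensitivity to the start pattern.** If starts fall linearly to zero over the window, the 2020 interval is 4–7% wider than at 1 May 2022. If they rise linearly from zero, it is 33–49% wider. For fulvestrant (median 9.5 months, uniform starts) it is 6% wider.

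**The case against.** **Reporting detail.** It can be said that the missing interval changes no estimate, that Protocol 9.8 commits to generally accepted methods, and that Protocol 9.5.1 already restrains small subgroups. All of that is true. But the shells define the deliverable, and a condition with no threshold that the SAP does not repeat cannot tell a reader how precise a printed median is.

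**Wrong clock.** The calculations run from palbociclib start, whereas PFS and OS are defined from relapse or stage IV disease. Second-line patients are included, so follow-up from the index date can exceed 48 months by an amount the documents do not give. This stands. The figures are illustrations, although the absence of an interval does not depend on them.

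**The PFS date is a choice.** It matches the 2017–2020 study period, and deaths may be recorded more currently than progressions; SAP Table 1 names a possible second source for death. This also stands. The documents do not show how far progression entry is complete. Protocol 9.1's end-of-2021 statement concerns which patients are included, so a reader should not take it as proof that later progression data exist.

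**Stronger readings that the documents do not support.**
- A reader might infer that the early cut biases median PFS. Administrative censoring alone does not.
- A reader might suppose that the same IQR would be printed at any sample size. At the 2020 cut the upper quartile would often be unreached at the longer medians, and the SAP's wording allows for that.
- A reader might fault the plan for being unable to separate a subgroup median from the published 20.0 or 24.8 months. No such comparison is planned.

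**Conclusion.** The main point holds without any modelling: neither SAP 7.2 nor Tables 4–6 plan a confidence interval for PFS, ToT or OS, and an IQR does not replace one. This should be corrected before analysis. Under the stated assumptions the uncertainty left unreported is about ±2 to 3 months for median PFS with 1,000 patients and ±5 to 8 months with 150.

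The cut-off point is real but secondary. The cost to the median's interval is modest (15–20% wider with uniform starts, 4–49% across the start patterns tried). The cost in AI PFS events (about 30%) is larger, as is the cost to the upper quartile if the true median is near 24.8 or 27.6 months. These sizes depend on the exponential shape, the start pattern and the use of palbociclib start as time zero. Whether the date should move depends on how complete progression entry is, which the documents do not show. The missing ToT cut-off, and the missing OS date in the SAP, are plain omissions.

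**What to change.** **Main change.** In SAP 7.2 and Tables 4–6:
- report every median, and every 6-, 12- and 24-month OS rate, with a 95% CI and the N for that row;
- mark unreached quartiles or confidence limits as not reached;
- carry the sample-size condition of Protocol 9.5.1 into SAP 4.1.

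This costs about two sentences of SAP text and extra entries in three shells. It needs no new data and is right whichever cut-off is used.

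**Secondary change.** Ask the register to what date progression data are complete. If that is later than 31 December 2020, censor PFS at the last complete date and keep 31 December 2020 as a sensitivity cut. If not, keep the date and say why. State the ToT cut-off, and put the protocol's 1 May 2022 OS censoring date into SAP 7.1. This costs one register query and wording in Protocol 8.1 and SAP 7.1. If the PFS date moves, a protocol amendment may be needed under Protocol 9.7; if it does not, the PFS part reduces to one sentence of justification.

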## 8 LIST OF TABLES AND TABLE SHELLS

This section presents an overview of the table shells.

**Table 2.** Descriptive statistics

Population	Subgroup	Outcome	Result
All included patients	-	Number of patients	N (100%)
		Age	Median, mean and st. deviation
All included patients	Patients younger than 50 years	Number of patients	N (%)
	Patients aged 50-70 years	Number of patients	N (%)
	Patients older than 70 years	Number of patients	N (%)
All included patients	Patients with visceral disease	Number of patients	N (%)
		Age	Median, mean and st. deviation
	Patients without visceral disease	Number of patients	N (%)
		Age	Median, mean and st. deviation
All included patients	Primary MBC	Number of patients	N (%)
		Age	Median, mean and st. deviation
	Recurrent MBC	Number of patients	N (%)
		Age	Median, mean and st. deviation

PFIZER CONFIDENTIAL

**Table 3.** Disease-specific descriptive statistics.

Population	Subgroup	Outcome	Result
All included patients	-	Type of metastases	Visceral: N (%) Non-visceral: N (%) Both: N (%)
		Number of metastases	0: N (%) 1: N (%) 2: N (%) >2: N (%)
		Location of metastases	Skin: N (%) Bone: N (%) Lung: N (%) Liver: N (%) CNS: N (%) Other: N (%)
		Surgery	Yes: N (%) No: N (%)
		Adjuvant treatment*	Type 1: Median number of treatments of type 1: Type 2: Median number of treatments of type 2:
All included patients	Patients younger than 50 years	Type of metastases	Visceral: N (%) Non-visceral: N (%) Both: N (%)
		Number of metastases	0: N (%) 1: N (%) 2: N (%) >2: N (%)
		Location of metastases	Skin: N (%) Bone: N (%) Lung: N (%) Liver: N (%) CNS: N (%) Other: N (%)
		Surgery	Yes: N (%) No: N (%)
		Adjuvant treatment*	Type 1: Median number of treatments of type 1: Type 2: Median number of treatments of type 2:

PFIZER CONFIDENTIAL

Patients aged 50-70 years	Type of metastases	Visceral: N (%) Non-visceral: N (%) Both: N (%)
	Number of metastases	0: N (%) 1: N (%) 2: N (%) >2: N (%)
	Location of metastases	Skin: N (%) Bone: N (%) Lung: N (%) Liver: N (%) CNS: N (%) Other: N (%)
	Surgery	Yes: N (%) No: N (%)
	Adjuvant treatment*	Type 1: Median number of treatments of type 1: Type 2: Median number of treatments of type 2:
Patients older than 70 years	Type of metastases	Visceral: N (%) Non-visceral: N (%) Both: N (%)
	Number of metastases	0: N (%) 1: N (%) 2: N (%) >2: N (%)
	Location of metastases	Skin: N (%) Bone: N (%) Lung: N (%) Liver: N (%) CNS: N (%) Other: N (%)
	Surgery	Yes: N (%) No: N (%)

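### SAP 7.2 tests each age group against the whole cohort that contains it, so an ordinary two-sample chi-square test gives p-values that are too large, mildly for a small group and severely for a large one

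*SAP*

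**What the plan says.** SAP 7.2 lists three pairs for testing: "all patients' vs. 'patients younger than 50 years", "all patients' vs. 'patients aged 50-70 years" and "all patients' vs. 'patients older than 70 years". For each pair a "statistical test (e.g". chi-square) is to be performed on two variables, "types of metastases' (visceral, non-visceral or both") and "surgery' (yes or no"). That makes six tests, two-category for surgery (1 df) and three-category for type of metastases (2 df).

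The age groups lie inside the full cohort. SAP 4.1 takes the one study population and says that "results will also be presented for the following subgroups", the three age bands among them. Tables 2 and 3 in SAP 8 list each age band as a subgroup under "All included patients".

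Neither document redefines the comparator as the remaining patients or names a method for overlapping samples. SAP 3 and 7 describe the study as descriptive, without formal hypotheses. No significance level is given.

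**The concern.** A two-sample chi-square test takes its two rows to be independent sets of patients. Here the smaller row is part of the larger one. The overlap pulls the two proportions together, while the test's variance formula treats the sample as bigger than it is. Both effects shrink the statistic.

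At stake is how the exploratory age comparisons are read. A real difference in metastatic pattern or surgery between age groups could be reported with an unremarkable p-value and taken as similarity. The shrinkage also depends on group size, so the three p-values for one variable would not be comparable with each other.

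**Working it through.** The documents give no p-value, level or age-group size for these tests, so there is no stated figure to reproduce.

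**Inputs.** From the documents: the three pairs and two variables (SAP 7.2), the nesting of the age groups (SAP 4.1 and 8), and N of about 1,500 (SAP 2.2; Protocol 9.5). Assumed: a two-sided nominal 5% level, the age share f, the underlying proportions and the differences.

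**Variance.** Let p be the common proportion under no difference and q = 1−p.

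- Group minus all = (1−f) × (group minus rest).
- Var(group − rest) = pq[1/(Nf) + 1/(N(1−f))] = pq/(Nf(1−f)).
- True Var(group − all) = (1−f)² × pq/(Nf(1−f)) = pq(1−f)/(Nf).
- Variance used by the ordinary test = pq[1/(Nf) + 1/N] = pq(1+f)/(Nf).

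The ordinary chi-square is therefore about (1−f)/(1+f) times the valid one.

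**True level at nominal 5%.** For 1 df it is 2[1 − Φ(1.96 √((1+f)/(1−f)))]. For 2 df it is the upper tail of chi-square with 2 df at 5.99 × (1+f)/(1−f).

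| f | shrinkage (1−f)/(1+f) | surgery (1 df) | type of metastases (2 df) |
|---|---|---|---|
| 10% | 0.818 | 0.030 | 0.026 |
| 1/3 | 0.500 | 0.0056 | 0.0025 |
| 50% | 0.333 | 0.0007 | 0.0001 |

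The age shares are unknown, but the three groups partition the cohort, so at least one holds a third or more. If an ordinary two-sample chi-square is used, at least one comparison per variable therefore has a true level of at most 0.0056 (surgery) or 0.0025 (type of metastases), whatever the age mix.

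**Simulation check.** With 400,000 replicates, groups of 225, 750 and 525 and p = 0.5, the overlapping test rejected at rates of 0.0223, 0.0007 and 0.0046. Testing each group against the rest rejected at 0.049 to 0.053.

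**Worked tables (no continuity correction).**

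- Large group, f = 50%. Against the rest, 435/750 vs 375/750: pooled 0.54, chi-square = 0.08²/[0.54 × 0.46 × (1/750 + 1/750)] = 9.66, p = 0.0019. Against all, 435/750 vs 810/1,500: pooled 1,245/2,250 = 0.553, chi-square = 0.04²/[0.553 × 0.447 × (1/750 + 1/1,500)] = 3.24, p = 0.072. The ratio is 3.24/9.66 = 0.335 (theory 0.333). This second table counts 2,250 patients in a cohort of 1,500.
- Small group, f = 10%. Against the rest, 90/150 vs 675/1,350: chi-square 5.40, p = 0.020. Against all, 90/150 vs 765/1,500: chi-square 4.42, p = 0.035. The ratio is 0.819 (theory 0.818).

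**Power (simulated, N = 1,500, one group deviating).**

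| f | base rate, difference | group vs all | group vs rest | three-group test |
|---|---|---|---|---|
| 50% | 50%, +8 points | 39% | 88% | 80% |
| 50% | 50%, +12 points | 90% | above 99% | 99% |
| 10% | 50%, +12 points | 74% | 80% | 71% |
| 50% | 10%, +8 points | 84% | 99% | 99% |

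**The case against.** **Little rests on these tests.** The study is descriptive, and the Table 3 shells show counts and percentages with no column for p-values. The correct age-specific percentages will be printed whatever test is run, and the error is conservative. This stands, and it limits the weight of the point. It does not remove it, because the SAP says the tests will be performed and an exploratory p-value should still be valid.

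**Chi-square is only an example.** That is true, and the levels above hold only for an ordinary two-sample chi-square. The comparison could instead be run as a one-sample test of the group against the full-cohort distribution. The shrinkage is then (1−f), and the levels at f = 1/3 are 0.016 (1 df) and 0.011 (2 df). That is milder but still too conservative. The fault is in the pairs, so changing to another ordinary two-sample test does not cure it.

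**The size depends on assumptions.** The 5% level, the base rates and the differences are ours. The power loss is much smaller at a 10% base rate (84% against 99%) than at 50% (39% against 88%). SAP 6 limits the analysis to patients with complete registrations, so N may be below 1,500. That would change the power and the worked p-values, but not the shrinkage or the large-sample levels.

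**Conclusion.** The concern holds. As worded, SAP 7.2 compares each age group with a set that includes it, and an ordinary two-sample test on those pairs gives p-values that are too large. The loss is mild for a small group and severe for a large one, and at least one of the three groups must hold a third or more of the cohort. The direction and the shrinkage factor need no assumption about the data beyond use of the ordinary two-sample test. The quoted levels assume a nominal 5%; the worked p-values and power also rest on assumed age shares, proportions and N.

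The consequence is confined to exploratory p-values for type of metastases and surgery by age. The plan should be corrected, but its main results do not depend on this.

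**What to change.** Reword the three comparisons in SAP 7.2 in one of two ways:

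1. One chi-square test per variable across the three mutually exclusive age groups (3×3 for type of metastases, 3×2 for surgery).
2. Each age group against all other patients.

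The full cohort can stay in Table 3 as a descriptive reference.

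The cost is SAP wording only, with the same data. Option 1 cuts six tests to two, but it does not say which group differs. It also has less power than option 2 when a single group deviates: 80% against 88% in the first row of the power table, and 71% against 80% in the third, where it falls slightly below the planned test's 74%. Option 2 keeps six tests.
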